## **SECTION 1: PURPOSE AND BACKGROUND OF THE RESEARCH**

Provide the scientific or scholarly rationale for the research. Describe the relevant background information and the specific gaps in current knowledge that this study intends to address.

The purpose of this research is to assist laser treatment of skin conditions by imaging the skin to obtain information about lesional skin. This is a pilot study that will explore the utility of skin imaging in guiding the laser treatment of skin lesions. This study will utilize Optical Coherence Tomography (OCT). Data acquisition of the skin will guide laser treatment by providing information on skin lesion characteristics.

There have been shown to be many applications for OCT. This imaging modality have been used to examine normal skin, burn scars, hemangiomas, nevus flammeus, fibrosarcomas, rosacea, and telangiectasias. Skin conditions to be studied include vascular lesions, scars, and inflammatory conditions. Normal and lesional skin will be assessed.

Currently, laser settings are selected without the assistance of imaging. Imaging with OCT provides more information about the characteristics of the skin lesion (such as lesion depth, depth of the most superficial part of the lesion, and the size and density of blood vessels), which could allow for more informed selection of laser settings to treat individual skin lesions. OCT has been used to examine laser treatments as well, but our proposed protocol would include the use of OCT to examine the stated skin lesions above before and after laser treatment in order to compare to prospective controls that did not undergo OCT imaging. The goal of our study is to optimize laser treatment with the assistance of OCT and guide future laser treatments. It has been shown that very early treatment of vascular lesions such as Port-Wine birthmark during infancy most often results in a better chance of lesion regression and can greatly improve the clinical and psychosocial well-being of the patient. Therefore, we will utilize OCT imaging, which is FDA-cleared for use on subjects of all ages to image our patient population.

The following imaging modalities will be used:

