### **2. Study Design**

Include an explanation of the study design (e.g., randomized placebo-controlled, cross-over, cross-sectional, longitudinal, etc.) and, if appropriate, describe stratification/ randomization/blinding scheme.

This is a longitudinal study with matched prospective controls. The patients will undergo treatment and follow-up over the course of 1-7 months. Their results will be compared to that of matched prospective controls with similar treatment and follow duration. There is no placebo, and patients will not be blinded.

Patients will be stratified based on their lesion type and the size of the lesion as these factors may impact the response to laser treatment and thus the data measurements from OCT. Photographs of the patients' treated lesions will be rated for lesion improvement by blinded physicians. OCT measurements of the lesion of interest will be used to validate the improvement and cosmetic results.

Provide precise definitions of the study endpoints and criteria for evaluation; if the primary outcomes are derived from several measurements (i.e., composite variables) or if endpoints are based composite variables, then describe precisely how the composite variables are derived.

Primary endpoints include photographic improvement of the lesion(s) of interest after 1 or more laser treatments. Two board certified dermatologists grade the degree of improvement (clearance of the lesion) in quartiles (no clearance=0-25, mild clearance=26-50, good clearance=51-75, excellent clearance=76-95, complete clearance=96-100). It will be up to the experienced treating dermatologist to determine the number of treatments necessary for maximum clearance of the lesion(s).

Secondary endpoints include measurements with OCT, which show reduced lesion thickness, lesion size, size of blood vessels, and density of blood vessels, and number of superficial blood vessels.

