##### Statistical Analysis Plan

Primary Objective: The outcome of degree of improvement will be compared between those previous patients that were treated conventionally as a prospective control and those prospective patients who will be treated with assistance from the OCT device. We will use a two-sample t-test to examine the difference in degree of improvement between the two groups at each treatment.

Secondary Objective: We will present the mean/standard deviation and 95% confidence interval of all secondary outcomes (including lesion thickness, size, size of blood vessels, and density of blood vessels, and number of superficial blood vessels.) at each treatment.

2. Describe the primary statistical method(s) that will be used to analyze the primary outcome(s) or endpoints.

N/A

3. Describe the secondary statistical method(s) that will be used to analyze the secondary outcome(s) or endpoints.

N/A

4. If appropriate describe secondary or post hoc analyses of primary outcome(s) or other exploratory analysis.

N/A

5. Sample Size Determination: Explain how the overall target sample size was determined (e.g., power analysis; precision estimation), providing justification of the effect size for the primary outcome based on preliminary data, current knowledge/literature and/or cost consideration; if appropriate, provide sample size justification for secondary outcomes. Power analysis should (at least) match the primary outcome/endpoint.

Literature indicated that laser treatment of skin lesions yields varying degree of clearance across different types of lesions. For example, the Ashinoff et al. 1991 study showed 50% lesion clearance after 3 laser treatments for port wine birthmarks in 12 infants. Another Ashinoff et al. 1991 study showed 70% lesion clearance after 3 laser treatments for capillary hemangiomas in 10 infants. The Clark et al. 2002 study showed 50% lesion clearance after 3 laser treatments for rosacea in 12 adults. Last but not least, the Geronemus 1991 study showed 90% lesion clearance after 1 laser treatment for spider telangiectases in 12 adults. Based on these data, we calculated a mean of 65% ( $\pm 20\%$ ) lesion clearance after 3 laser treatments for any lesion type. Adjusting for the unique characteristics of our patient population at UCI, we estimated a mean lesion clearance of 40% ( $\pm 20\%$ ) after 1 laser treatment for any lesion type.

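### OCT is given the role of validating photographic improvement, but the only planned OCT analysis is group summaries, which cannot show whether OCT change tracks the blinded grade within patients

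*Combined protocol and SAP*

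**What the plan says.** **Role of OCT.** Section 6, Study Design: "OCT measurements of the lesion of interest will be used to validate the improvement and cosmetic results". The secondary endpoints are five OCT measures: lesion thickness, lesion size, vessel size, vessel density and number of superficial vessels. None is named as the main one.

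**Analysis of OCT.** Statistical Analysis Plan, Secondary Objective: "We will present the mean/standard deviation and 95% confidence interval of all secondary outcomes", at each treatment.

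**Analysis of the photograph grade.** Same section, Primary Objective: "We will use a two-sample t-test to examine the difference in degree of improvement between the two groups at each treatment". OCT does not enter this analysis. The form's further items on primary and secondary methods are answered N/A, as is the prompt "If appropriate describe secondary or post hoc analyses of primary outcome(s) or other exploratory analysis".

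**Masking.** Study Design: "Photographs of the patients' treated lesions will be rated for lesion improvement by blinded physicians" and "There is no placebo, and patients will not be blinded". Nothing is said about who measures the OCT images or what they know when they do so.

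**Who has OCT.** Section 1 describes OCT "before and after laser treatment in order to compare to prospective controls that did not undergo OCT imaging". Under Research Procedures, study patients are photographed and scanned at visit one and at follow-ups every 4 weeks (1 to 6 of them). The same section says that some patients may be asked to more than one imaging session and may refuse.

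**The concern.** To say that OCT validates a clinical grade is to make a statement about individual patients: lesions graded as more cleared should show larger OCT reductions. The plan holds both halves of the evidence on the same patients but never joins them. A report that followed it would give a table of OCT means and a separate t-test on grades. It could not say whether the two agree, although the Study Design section says that OCT will be used in this way. The form also asks that the analysis plan match the stated aims.

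At stake is a secondary claim of a pilot study. The likely error is a report that treats a fall in mean OCT values beside a good mean grade as validation, when no such relation was examined.

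**Working it through.** **1. The plan's own figure.** Sample Size Determination: 60% against 40% clearance, SD read as 20 points from the stated ±20%, two-sided 5%, 80% power.
- Normal approximation: n per group = 2(1.960 + 0.842)² × (20/20)² = 15.7, so 16.
- Noncentral t: 16.71, so 17. Power at 17 per group is 80.7%.

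The stated 17 per group reproduces. It is sized for the photograph comparison. No precision or power is given for any relation between OCT and the grade.

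**2. What the planned OCT summaries can show.** Let d be a patient's OCT change and g the grade. Shuffle the g values among the study patients. Every mean, SD and CI of the OCT outcomes is unchanged, and so is the group mean grade and the t-test. The correlation of d with g can move across its whole range. The planned output therefore carries no information on that correlation.

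Per-visit summaries do not give the precision of the change either. SD(d) = √(s₀² + s₁² − 2ρs₀s₁), where s₀ and s₁ are the SDs at the two visits and ρ is the within-patient correlation between them. The plan does not report ρ.

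**3. What a paired analysis could deliver.** Pairs exist in the study group only: 17 at the planned size, and 30 at the consent maximum in Section 3. The documents give no correlation, so the r values below are assumptions. Fisher z: 95% CI = tanh(atanh(r) ± 1.96/√(n − 3)). At n = 17, 1/√14 = 0.267.

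| Assumed r | 95% CI, n = 17 | Power, n = 17 |
|---|---|---|
| 0 | −0.48 to 0.48 | – |
| 0.4 | −0.10 to 0.74 | about 35% |
| 0.5 | 0.03 to 0.79 | about 54% |
| 0.6 | 0.17 to 0.84 | about 74% |
| 0.8 | 0.52 to 0.92 | – |

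Power is Φ(atanh(r)√14 − 1.96). For r = 0.6: 0.693 × 3.742 − 1.96 = 0.63, giving about 74%.

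- Correlation needed for 80% power: tanh((1.960 + 0.842)/√14) = tanh(0.749) = 0.63. With 30 pairs it is about 0.49.
- Spearman standard error (Bonett–Wright), √((1 + r²/2)/(n − 3)): at r = 0.6 this is √(1.18/14) = 0.290, and the CI widens to about 0.12 to 0.85.
- If refusals left 12 pairs (an illustration): 0.693 ± 1.96/3 gives 0.04 to 0.87 at r = 0.6.
- Five measures each tested at 5% would give a false-positive chance of 1 − 0.95⁵ = 23% if independent. This is why one measure should be named in advance.

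**The case against.** The best reply is that OCT is in this trial mainly to guide laser settings. That is its purpose in the summary, in Section 1 and in Research Procedures. Neither the hypothesis nor the two statistical objectives contain a validation aim. The word appears in one sentence and may mean only supportive description. This stands as a reason to keep the point modest, and to accept rewording as a full answer. It does not close the gap, because group means beside a grade still do not show agreement.

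Four stronger readings are tempting, and the documents do not support them.

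- *That OCT is read unmasked and biased toward reduction.* The plan is silent on this. It does not say who measures the scans, whether measurement is manual or automated, or what is concealed. Section 2, where the form places study-team qualifications, is not in the text reviewed. That the treating team uses the scans to choose settings makes the question fair, but shows no defect. A masked re-read by that same team is also not plainly free of cost.
- *That the plan claims OCT validates the difference from controls.* The Study Design sentence speaks of the lesion of interest. The Section 1 wording, "in order to compare to prospective controls that did not undergo OCT imaging", is loose, and can be read as comparing treatment results with those of controls who were not scanned.
- *That validation is out of reach.* Only the planned analysis lacks it. The paired data are to be collected.
- *That 17 pairs can separate real tracking from none.* The intervals at r = 0.6 and r = 0 overlap from 0.17 to 0.48, and power at 0.6 is about 74%.

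A simple pooled correlation of raw changes would also be weak. Study Design itself warns that lesion type and size may affect response and OCT measurements, so the result could reflect lesion mix.

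**Conclusion.** The point holds as a mismatch between a stated use of OCT and the stated analysis. As written, the plan gives no information on whether OCT change follows the blinded grade within patients. A paired analysis in the study group would supply an estimate, but an imprecise one: about 0.17 to 0.84 at an assumed r of 0.6 with all 17 pairs, slightly wider with a Spearman standard error, and wider still if repeat imaging is refused. These figures assume one pair per patient and ignore ties on the five-level grade.

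The evidence can apply only within the study group, since controls have no OCT. Masking of OCT reading is a point to clarify, not a shown fault. The primary comparison and its sample size are untouched. The change is worth making because it costs little, not because the trial depends on it.

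**What to change.** In the Secondary Objective of the Statistical Analysis Plan:

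1. For study-group patients, report the within-patient percent change from the baseline pre-laser scan in each OCT measure, with a 95% CI.
2. Name one main OCT measure and one follow-up visit in advance, and specify which scan at that visit is used relative to any further laser. Relate the change in that measure to the blinded photograph grade from the same visit by Spearman correlation with a 95% CI, one pair per patient. Combine the two dermatologists' grades by the same rule as in the primary analysis. Show the result also by lesion type. Treat the other four measures as exploratory.
3. State that this is estimation only, give the expected precision at 17 pairs, and report how many patients lack a repeat scan.

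In Study Design, state that the OCT evidence applies within the study group only. If the paired analysis is not added, replace 'validate' with 'describe alongside'. State also who measures the scans, and whether they are masked to visit and grade.

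Cost: SAP wording, a little extra analysis, and a narrower claim for OCT. No new patients, visits or scans are needed. Any masked second reading, if chosen, would be a separate cost.

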Multiple centers in the US and Europe have started using OCT to provide information about the skin. The PI participated in one study where information was gathered.

This information is not yet being used commonly to guide laser treatments.

Describe the purpose, specific aims or objectives. Specify the hypotheses or research questions to be studied.

The purpose of this research is to assist laser treatment of skin conditions by imaging the skin to obtain information about lesional skin. This is a pilot study that will explore the utility of skin imaging in guiding the laser treatment of skin lesions. The current standard of laser treatment without the assistance of imaging is to treat patients based on qualitative, visual characteristics of the skin lesion, such as vascularity, pliability, height, and pigmentation of the lesion. Imaging with OCT provides more information about the characteristics of the skin lesion (such as lesion depth, depth of the most superficial part of the lesion, and the size and density of blood vessels), allowing for more precise adjustment of laser settings to treat individual skin lesions. Laser treatment will be used within the approved normal parameters consistent with the standard of care. Our hypothesis is that treatments with the assistance of the OCT device will exhibit improvement of their lesions with few side effects.

Describe the primary outcome variable(s), secondary outcome variables, and predictors and/or comparison groups as appropriate for the stated study objectives/specific aims.

Primary outcome variables include assessment of photograph improvement. Two board certified dermatologists will grade the degree of improvement (clearance of the lesion) in quartiles (no clearance=0-25, mild clearance=26-50, good clearance=51-75, excellent clearance=76-95, complete clearance=96-100).

Secondary outcome variables: repeat measurements with OCT, including lesion thickness, size, size of blood vessels, and density of blood vessels, and number of superficial blood vessels.

List up to ten relevant references/articles to support the rationale for the research. Do not append an extensive NIH-grant-style bibliography.

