Some subjects may be asked to participate in more than one imaging session. They will have the option of refusing participation in additional sessions. Follow-up examinations will be performed every 4 weeks. During these examinations, photography and imaging of the lesion of interest will be performed with optional laser treatments to be performed at the discretion of the treating physician and the patient. If no laser treatment is necessary, then the visit should take no more than 30 minutes for a quick follow-up and imaging. Additional laser treatment will require no more than 30 minutes to complete. The number of follow-ups is also determined at the discretion of the treating physician and the patient but could range from 1 to 6 depending on the response of the lesion to treatment.

Matched prospective controls will be gathered to be compared against the imaged, treated, experimental group. The prospective controls will be matched to age, gender, skin type, and type of skin lesion. They will be gathered via a retrospective chart review by abstracting and data directly from our own records.

Describe the duration of a subject's participation in the study. If there are sub-studies, include duration of participation in each sub-study.

For each visit: history and skin examination-30 minutes, imaging – up to 30 mins, and laser treatment – up to 30 mins. These are all maximums and will likely be shorter.

At a follow-up, the patient may or may not receive a laser treatment thus shortening the visit. A patient would be expected to have 1-6 follow ups depending on their response to treatment, so their maximum time in this study could range from about 1 to 6 months. Each follow-up visit is made about 4 weeks from the prior visit.

List data collection instruments (e.g., measures, questionnaires, interview questions, observational tool, etc.).

*Investigator-authored, non-standardized, or un-validated measures must be submitted for review.*

Standardized photography,  
OCT

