The two studies of laser treatment with OCT imaging assistance, Weibel et al. 2016 and Weibel et al. 2018, demonstrated that the depth of lesions and the size and density of the surrounding blood vessels varied widely across patients with burn and traumatic scars and vascular hemangiomas, and that some lesions appearing to be superficial had a much deeper component than could be visualized or palpated. Based on this insight, we hypothesized that laser treatment with imaging assistance would enable dermatologists to calibrate the laser parameters precisely to the actual depth of a lesion and the actual size and density of the surrounding blood vessels; as a result, at least 60% ( $\pm 20\%$ ) of the lesion of any type would be cleared after one laser treatment with imaging assistance as compared to 40% ( $\pm 20\%$ ) without imaging assistance.

A sample size of 34 patients, including 17 patients prospectively treated with laser and imaging assistance for lesions of any type and 17 prospective controls who received laser treatment without imaging assistance, would yield 80% power to test the aforementioned hypothesis using a two-sided two-sample t test at 5% significance level.

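### The primary endpoint is a five-band grade from two dermatologists, but the 80% power is computed for a t-test on percentage clearance; the analysed variable needs defining, and a single grade could lose about 5 points of power

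*Combined protocol and SAP*

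**What the plan says.** **Endpoint.** Section 1 (primary outcome variables) states: "Two board certified dermatologists will grade the degree of improvement (clearance of the lesion) in quartiles". Section 6, Study Design, repeats this, saying that the two dermatologists "grade the degree of improvement (clearance of the lesion) in quartiles (no clearance=0-25, mild clearance=26-50, good clearance=51-75, excellent clearance=76-95, complete clearance=96-100"). The bands are called quartiles, but there are five and their widths differ. The same section says that photographs "will be rated for lesion improvement by blinded physicians".

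**Analysis.** The Statistical Analysis Plan, Primary Objective, says: "We will use a two-sample t-test to examine the difference in degree of improvement" between the two groups at each treatment. The next item on the form, which asks for the primary statistical method, is answered N/A.

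**Sample size.** For conventional treatment the text says "we estimated a mean lesion clearance of 40"% (±20%) after one treatment. With imaging, at least 60% (±20%) "of the lesion of any type would be cleared after one laser treatment with imaging assistance". With 17 patients per group, this "would yield 80% power to test the aforementioned hypothesis using a two-sided two-sample t test at 5% significance level".

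**Not stated.** The documents give no numeric score for the bands, no instruction that raters record a percentage, and no rule for combining the two ratings. They also do not say whether ±20% describes an underlying percentage, one rater's value, a two-rater mean or a graded score.

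**The concern.** The endpoint is defined on one scale and the power is calculated on another. The form's own prompt under Sample Size Determination asks that the power analysis match the primary endpoint. Sorting a percentage into five bands discards information, so a calculation that holds for the percentage need not hold for the grade.

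The variable entering the primary t-test is also left open. It could be a 0-4 code, a band midpoint or a percentage, and it could come from one rater, an agreed grade or an average. Any one of these, fixed in advance, would give a valid test. Left unfixed, the choice could be made after the ratings are seen, and the 80% is not tied to any one of them.

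**Working it through.** **Inputs from the documents.** Means 60 and 40, ±20 read as the standard deviation (SD), 17 per group, two-sided 5% two-sample t-test (Sample Size Determination); five bands (Study Design).

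**Assumptions.** Clearance is normal on an underlying percentage scale. Bands are cut at 25.5, 50.5, 75.5 and 95.5. Bands are scored either 0-4 or at midpoints 12.5, 38, 63, 85.5 and 98. Inter-rater correlations of 0.9, 0.7 and 0.5 are used only in step 6; the documents give none.

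**1. The plan's own figure.** Standardised difference d = (60 − 40)/20 = 1. Noncentrality = d × √(n/2) = √8.5 = 2.92 on 32 degrees of freedom. Exact power is **80.7%**, so the stated 80% is reproduced for a percentage.

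**2. The same patients in bands.** Each band's probability is the difference between normal distribution values at adjacent cuts.

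| Band | 0-25 | 26-50 | 51-75 | 76-95 | 96-100 |
|---|---|---|---|---|---|
| Mean 40 | 0.234 | 0.466 | 0.262 | 0.035 | 0.003 |
| Mean 60 | 0.042 | 0.275 | 0.463 | 0.181 | 0.038 |

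With midpoint scores the means are 40.4 and 59.4 (difference 19.0) and the SDs are 20.0 and 20.1, so d = 0.947. With 0-4 codes the means are 1.106 and 1.897 and the SDs are 0.806 and 0.876, so d = 0.940.

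**3. Power for one grade, 17 per group.** Simulation (200,000 trials) gives 75.5% for codes and 75.5% for midpoints, against 80.6% for the percentage in the same runs. **One grade gives about 76%, a loss of about 5 points**, before any rater error. With 19 per group, one grade reaches 80% (80.3% codes, 80.4% midpoints).

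**4. Type I error.** With both means at 40, rejection rates are 5.0% (percentage), 5.1% (codes) and 5.0% (midpoints). Banding does not bias the test.

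**5. If ±20% already describes graded scores.** Setting the midpoint scores themselves to means 60 and 40 with SD 20 gives 79.8%, so there is essentially no loss.

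**6. Averaging two raters.** Power at assumed correlations 0.9 / 0.7 / 0.5:

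| What ±20% describes | Mean of two grades | Mean of two percentages |
|---|---|---|
| The two-rater mean | 78 / 78 / 78% | 81 / 81 / 81% |
| One rater's percentage | 80 / 84 / 88% | 83 / 87 / 90% |
| Clearance before rater error, which adds to it | 76 / 70 / 61% | 79 / 73 / 64% |

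Within each reading, the mean of two percentages is about 3 points above the mean of two grades (2.6 to 2.9). How far either lies from 80% depends on what ±20% describes and on rater agreement.

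**7. Rounding.** If percentages are rounded to the nearest 5, power is 80.5%; to the nearest 10, 79.8%.

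**The case against.** The strongest reply is that there may be no mismatch. The bands are cut-points on a 0-100 clearance scale, and the sample size text describes the same quantity. Raters may record a percentage that is only labelled with a band; the 80.7% would then stand. The rating form could settle this, but it is not among the documents reviewed. Likewise, if ±20% came from graded scores, step 5 shows no loss. Both readings are open, but the documents state neither.

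The second reply is size. Five points is small beside the uncertainty in a 20-point effect that is a hypothesis, and in a 40% control mean that was adjusted by judgement, in a self-described pilot. The enrolment table also allows 30 consented per group against 17 needed. This stands, and it is why the point is an improvement rather than a fatal flaw.

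The third reply is that a sentence fixing the score and the two-rater rule would close the gap without a new rating field. That is a sound fallback. Recording a percentage goes further because it avoids the banding loss at little cost.

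A reader might infer more than the documents support:

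- **That the 80% was miscalculated.** It was not (step 1).
- **That a t-test on grades is invalid.** Type I error is kept for any one fixed score (step 4).
- **That the trial's true power is well below 80%.** Such figures need an assumed rater error, and the lowest also need one of the two assigned raters to be ignored. The documents support neither assumption.
- **That the missing two-rater rule always matters more than the banding.** At a correlation of 0.9, averaging gains about 2 points on percentages and about 4 on grades, while banding one grade costs about 5. The ranking depends on agreement and on the order in which the steps are counted.

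**Conclusion.** The concern holds in a limited form. The 80% is right for percentage clearance but is not shown for the endpoint as defined. If ±20% is the SD of an underlying percentage, a single five-band grade has about 76% power with 17 per group before rater error. Averaging two grades recovers some or all of the banding loss, depending on rater agreement. The test is not biased. The 76% rests on a normal underlying percentage and on the assumed cuts and scores. An agreed (consensus) grade was not modelled, so no figure is given for it. The main gain from acting is a primary variable that is defined in advance and somewhat more precise.

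**What to change.** **Preferred.** Have the same two blinded dermatologists each record 0-100% clearance from the photographs already to be rated. Define the primary variable as the mean of the two and keep the planned two-sample t-test. Report the five bands and rater agreement descriptively. State which variable ±20% describes.

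**If only grades are kept.** State the band score (for example midpoints) and the two-rater rule (for example the average), and restate power for that variable. Under the underlying-percentage reading this is about 76% for one grade, and 19 completers per group would bring it to 80%. For averaged grades, give a range over assumed rater agreement.

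**Cost.** The change needs one field on the rating form and a sentence each in the endpoint and analysis text, with no extra raters or visits. Raters will round, which costs about 0 to 1 point of power. Visual percentage estimates carry rater error, which averaging reduces but does not remove. Rating the controls needs usable photographs. Research Procedures says of the controls: "They will be gathered via a retrospective chart review". Nothing in the documents confirms that photographs exist for them. The banded plan has the same dependence, so this should be checked either way.

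### The primary clearance scale has no grade for a lesion worse than baseline, so worsening scores the same as little or no response, and no other between-group endpoint captures it

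*Combined protocol and SAP*

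**What the plan says.** Section 1 introduces the endpoint: "Primary outcome variables include assessment of photograph improvement". It continues: "Two board certified dermatologists will grade the degree of improvement (clearance of the lesion) in quartiles". The bands, identical in Section 1 and in Section 6 (2. Study Design), are: "no clearance=0-25, mild clearance=26-50, good clearance=51-75, excellent clearance=76-95, complete clearance=96-100". Study Design gives the raters' task: "Photographs of the patients' treated lesions will be rated for lesion improvement by blinded physicians". Neither section says what to record when a lesion looks worse.

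The Statistical Analysis Plan in Section 6 reads: "We will use a two-sample t-test to examine the difference in degree of improvement between the two groups at each treatment". It does not say whether the band or a percentage is the analysed variable. The sample-size text uses percentages. For controls, "we estimated a mean lesion clearance of 40% ( $\pm 20\%$ ) after 1 laser treatment for any lesion type"; for the imaging group, "at least 60% ( $\pm 20\%$ ) of the lesion of any type would be cleared after one laser treatment with imaging assistance".

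On scope, Section 1 states: "Skin conditions to be studied include vascular lesions, scars, and inflammatory conditions". The hypothesis in the same section expects improvement together with few side effects. The secondary endpoints are OCT measurements, which Study Design words as reductions and the analysis plan only describes. Section 1 says the controls do not have OCT. The data collection instruments listed under Research Procedures are photography and OCT.

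**The concern.** The scale runs in one direction, from 0 to 100. A rater who sees a lesion that has deteriorated has no box for it and will presumably use the lowest band, where it joins lesions that did not change and lesions that cleared by up to a quarter.

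This matters because imaging is meant to alter laser settings lesion by lesion. A change of that kind could shift both ends of the response distribution: more lesions clearing well, and possibly more or fewer looking worse. The blinded photograph grade is the only outcome that the plan compares between the groups. If it merges worsening with weak response, the pilot cannot report how many lesions became worse in either group, and the mean of a group with worsened lesions is flattered.

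**Working it through.** **Inputs.** From the Statistical Analysis Plan: control mean 40, imaging mean 60, SD 20 in both, 17 per group, two-sided 5% t-test, 80% power. From Study Design: the five bands. Not in the documents, so assumed where used: how bands are scored, and how often and by how much lesions worsen.

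**The plan's own figure.** The standardised difference is (60 − 40)/20 = 1. The normal approximation gives 2 × (1.960 + 0.842)² / 1² = 15.7, so 16 per group. The noncentral t gives 16.71, so 17 per group, with power 80.7%. The stated 34 patients reproduce and are not in dispute.

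**How three lesions are scored.**

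| True change | Grade coded 0–4 | Percent floored at 0 | Band midpoint | Signed percent |
|---|---|---|---|---|
| 25% worse | 0 | 0 | 12.5 | −25 |
| Unchanged | 0 | 0 | 12.5 | 0 |
| 25% cleared | 0 | 25 | 12.5 | 25 |

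All three tie on the grade or midpoint. On the floored percentage only the first two tie.

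**Effect of one lesion 25% worse on a 17-patient mean.**
- Percent floored at 0: (0 − (−25))/17 = 25/17 = 1.5 points; 1.5/20 = 7% of the planned difference.
- Band midpoint: (12.5 − (−25))/17 = 37.5/17 = 2.2 points; 2.2/20 = 11%.
- Two such lesions: 50/17 = 2.9 to 75/17 = 4.4 points (15% to 22%).

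**Flooring under the plan's own normal distributions.** The share below 0 is Φ(−2) = 2.3% of controls (0.39 of 17 patients) and Φ(−3) = 0.13% of imaging patients (0.02 of 17). Flooring lifts a mean by SD × [φ(z) − z(1 − Φ(z))], where z is the mean divided by the SD:
- Controls: 20 × (0.0540 − 2 × 0.02275) = 0.17 points.
- Imaging group: 20 × (0.00443 − 3 × 0.00135) = under 0.01 points.

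The net effect is about 0.16 points, 0.8% of 20, and it raises the control mean.

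**Compression if some imaging-group lesions worsen.** Assumption, not in the documents: a share w of imaging-group lesions ends at −30%, the rest follow N(60, 20), and controls follow N(40, 20). Simulation with 17 per group, 40,000 runs, values capped at 100 and grades coded 0–4:

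| w | Mean difference: signed / floored / grade | Probability of a significant result favouring OCT: signed / floored / grade |
|---|---|---|
| 0 | 19.8 / 19.6 / 0.79 | 0.81 / 0.81 / 0.75 |
| 10% | 10.9 / 13.7 / 0.60 | 0.26 / 0.40 / 0.46 |
| 30% | −7.1 / 1.7 / 0.22 | 0.01 / 0.04 / 0.09 |

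At w = 10% the signed difference keeps 10.9/19.8 = 55% of its size, while the grade difference keeps 0.60/0.79 = 76%. At w = 30% the signed mean is against OCT while the grade mean still favours it.

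**Can the test still show a worse result with OCT?** With the planned means reversed (imaging 40, control 60), the probability of a significant result against OCT is 0.81 on percent and 0.76 on grades. It can.

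**The case against.** A reader might infer that the primary comparison cannot register harm at all. The documents do not support that. A worsened lesion takes the lowest score and pulls its group's mean down, and the planned test is two-sided. Worsening is attenuated; it does not disappear.

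The size is also open to challenge. Under the plan's own distributions hardly any lesion falls below 0, and the resulting bias is about 0.16 points in the direction unfavourable to OCT. The share of patients in the lowest band does not help the concern, because most of that band is lesions between 0 and 25 that the scale handles as intended. The 2.2-point figure needs midpoint scoring, which the plan never states, and 12.5 of its 37.5 points comes from band width, which would credit an unchanged lesion as well. The simulated effects rest on assumed worsening in one group only. No section says how often lesions look worse after laser, and Sections 1 and 6 keep treatment within standard care. All of this stands, and it limits the point to one about measurement. It does not show that worsening is rare, since the planning normals were not built to describe it.

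A reader might also infer that side effects go unrecorded. That cannot be concluded: Section 7 refers risks to the consent form, which is not part of the reviewed text. What can be said is that no side-effect or worsening outcome appears among the endpoints or in the analysis plan. The response-to-treatment item screened for controls in Section 3 is a screening variable and is not named as an outcome.

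Finally, this is a pilot whose stated construct is clearance. That lowers the stakes. It does not explain why raters who see a worse lesion should have no way to say so.

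**Conclusion.** The point holds in a limited form. The scale, defined identically in two places, cannot separate a worsened lesion from one unchanged or up to 25% cleared when the grade is analysed, or from an unchanged one when a percentage floored at 0 is analysed. No other between-group endpoint separates them, because OCT measurements exist in one group only and no side-effect outcome is listed.

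The size depends on how many lesions worsen, which the documents do not give. Per lesion 25% worse, the affected group's mean is overstated by 1.5 to 2.2 points; the range reflects the unstated choice between percent and grade and, at its upper end, assumed midpoint scoring. If worsening is as rare as the planning distributions imply, the effect on the primary result is negligible. If it is concentrated in one group, the effect could be material. The design as written would not show which case applies.

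**What to change.** Add a worse-than-baseline grade below the lowest band in both places where the scale is defined. The same two blinded dermatologists assign it, from the photographs that the primary comparison already requires in both groups.

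State in the Statistical Analysis Plan whether the grade or a percentage is analysed, and code worsening to match: one step below the lowest grade, or a signed percent change. With grades one step apart, each worsened lesion then moves a 17-patient mean by 1/17 = 0.06 grade. Report the number and proportion worse in each group next to the primary comparison, so that the reader does not depend on the coding.

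The cost is one more box on the grading form and a short addition to the analysis plan, with no extra visits, readers or photographs. The small downside is slightly less comparability with published quartile scales; collapsing the new grade into the lowest band in a supporting table would recover it.
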